2. OBJECTIVES AND ENDPOINTS

2.1 PRIMARY OBJECTIVE

The primary objective is to evaluate the efficacy of both the combination therapy of baloxavir with oseltamivir and that of oseltamivir plus placebo in SCT patients with influenza as measured by changes in influenza viral RNA loads at day 10 from baseline (day 1) and compare between arm differences in decline of viral load

The co-primary efficacy endpoints are:

- Change of influenza viral RNA loads from baseline (day 1) at the end of treatment (day 10) as measured by quantitative real time polymerase chain reaction (qRT-PCR, nucleic acid).
- Between-treatment-arm difference in the change of influenza viral RNA loads from baseline (day 1) at the end of treatment (day 10) as assessed by quantitative real time polymerase chain reaction as measured by (qRT-PCR, nucleic acid) and by Influenza plaque assay (replicating virus).

The secondary efficacy endpoints are:

1. **Change of influenza viral RNA load from baseline (day 1) at day 4 and day 7 and 10** as measured by quantitative real time polymerase chain reaction (qRT-PCR, nucleic acid) in each treatment arm.
2. **Difference in change of influenza viral loads from baseline (day 1) at day 4, 7 and 10 between the two treatment arms** as measured by quantitative real time polymerase chain reaction (qRT-PCR, nucleic acid)
3. **Change of influenza viral loads from baseline (day 1) at day 4, 7 and 10** as measured by Influenza plaque assay (replicating virus) in each treatment arm.
4. **Difference in change of influenza viral loads from baseline (day 1) at day 4, 7 and 10 between the two treatment arms** as measured by Influenza plaque assay (replicating virus).
5. **Time to Improvement of Individual Influenza Symptoms** [Time Frame: From Day 1 pre-treatment up to Day 30] defined as the time from the initiation of the study treatment to the improvement of influenza symptoms as assessed by patient-reported outcome measures on a single scale as specified in section 4.5.7. Time to improvement of symptoms is defined as the time from the start of treatment to the time when each of the influenza symptoms will be alleviated, maintained, or improved, for a duration of at least 24 hours.

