3. STUDY DESIGN

3.1 DESCRIPTION OF THE STUDY

This is a randomized double-blind placebo-controlled pilot study of the efficacy and safety of baloxavir in combination with oseltamivir (SOC) for the treatment of influenza in allogeneic stem cell transplant patients.

30 SCT recipients with influenza will take part in the study. Participants will be randomly assigned (1:1) to either baloxavir + oseltamivir or baloxavir-matched placebo +oseltamivir. Randomization will be performed by research pharmacy using an interactive web randomizer. Before randomization, patients will be stratified by hospitalization status (yes or no), influenza type A (yes or no).

Patients in the baloxavir combination arm will receive weight-adjusted baloxavir (40 mg for patients weighing <80 kg and 80 mg for those weighing \geq 80 kg) at baseline and at day 4 and day 7. They will also receive oseltamivir 75 mg twice daily for 10 days.

Patients in the baloxavir-matched placebo + oseltamivir arm will receive baloxavir-matched placebo at baseline and at day 4 and day 7 and oseltamivir 75 mg twice daily for 10 days.

Nasopharyngeal swabs will be collected on days 1 (at diagnosis, pre-meds), 2, (optional visit), 4, 7 and 10 for viral quantitation and viral sequencing. Influenza virus polymerase and neuraminidase sequencing will be also performed in all patients. Patients will have follow-up visits day 15 (+/- 2 days) and day 30 (+/- 2 days, EOT). Patients who will not clear the virus by day 10 will perform additional NP swabs at these visits.

Paracetamol (acetaminophen; maximum 3000 mg per day) or NSAIDS can be given for severe discomfort or fever. No other antiviral drugs for the treatment of influenza, will be permitted, except antibiotics for the treatment of suspected bacterial infections.

For the first 10 days, patients will receive a daily call from one member of the study team to review symptoms and severity scale.

To assess the **time to improvement of individual influenza symptoms** (with modification for preexisting symptoms), participants will be given a diary to self-assess the severity of seven influenza-associated symptoms on a four-point scale. To evaluate patient-reported **time to return to pre-illness health status**, patients will also rate **daily the interference of influenza symptoms in daily activities** on a 5-point severity scale.

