4.2 SAMPLE COLLECTION AND PROCESSING

4.2.1 NASOPHARYNGEAL SAMPLING AND VIROLOGICAL ASSAYS

Two nasopharyngeal swabs will be collected at each visit and put immediately into viral transport medium and frozen. Pharyngeal swabs will be collected when if it is not possible to collect nasopharyngeal swabs. At the end of the clinical study period, samples will be used for viral sequencing and virological assessment.

Viral RNA in pre- and last post-treatment swab samples will be extracted using conventional RNA extraction kit without virus amplification and used for viral RNA quantification by q-PCR and for viral sequencing. Swabs will also be used to calculate viral titers by plaque assays on MDCK cells.

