4.3 METHOD OF TREATMENT ASSIGNMENT

Participants will be and randomly assigned (1:1) to either the baloxavir + oseltamivir group, or the placebo + oseltamivir group. Before randomization, patients will be stratified by hospitalization (yes or no), influenza type A (yes or no). To maintain blinding, patients in the oseltamivir group will receive baloxavir-matched placebo.

The design randomization schema will be developed and managed by the Weill Cornell investigational pharmacy. Unblinding will be done when last patient completed the study follow up period.

Study Treatment: The investigational medicinal product (IMP) for this study is baloxavir in combination with oseltamivir.

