Each Party shall monitor and, as applicable, request feedback from the other Party regarding AE report timeliness in accordance with its own procedures. The Parties agree to provide written responses in a timely manner to inquiries from the other Party regarding AE reports received outside the agreed upon Agreement timelines. If there is any detection of trends of increasing or persistent non-compliance to transmission timelines stipulated in this Agreement, both Parties agree to conduct ad hoc or institute a regular joint meeting to address the issue.

In case of concerns related to non-compliance of processes, other than exchange timelines, with this Agreement, the Parties will jointly discuss and collaborate on clarifying and resolving the issues causing non-compliance. Every effort will be made by the non-compliant Party to solve the non-compliance issues and inform the other Party of the corrective and preventative actions taken.

Upon justified request, given sufficient notice of no less than sixty (60) calendar days, an audit under the provisions of this Agreement can be requested by either Party. The Parties will then discuss and agree in good faith upon the audit scope, agenda and execution of the audit. The requesting Party will bear the cost of the audit.

STATISTICAL CONSIDERATIONS

The study plans to enroll a total of 30 allogeneic bone marrow transplant patients who will be randomized at 1:1 to the two study arms. The primary endpoint data will be analyzed on the basis of a modified intention-to-treat (ITT) principle for patients with viral loads measurements at both the baseline and day 10.

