For the first co-primary objective, the effects of the study drugs will be evaluated separately for each study arm by estimating the change in viral RNA loads from baseline (day1) at the end of treatment (day10) as measured by qRT-PCR. Summary statistics including mean, standard deviation, median and range of the primary endpoints will be calculated for each arm. Difference in log transformed viral RNA loads measured at the end of treatment and at baseline will be evaluated using paired t-test or the Wilcoxon signed rank test for each arm separately. For the second co-primary endpoint, efficacy of the baloxavir + oseltamivir will be assessed through estimating the differences in the magnitude of change in viral RNA loads from baseline at the end of treatment between the two treatment arms along with the 95% confidence intervals. Given the pilot nature of the study, the sample size is primarily based on feasibility and logistic considerations. However, based on prior studies [ref: Infect Dis Ther (2019) 8:613–626], the expected baseline viral RNA loads for the immunocompromised patients would be around $6.5 \log_{10} \text{vp/mL}$ with standard deviation around $3 \log_{10} \text{vp/mL}$. With 15 patients in a study arm, we would have 80% power to detect a difference of $2.33 \log_{10} \text{vp/mL}$ in viral RNA loads at the end of treatment vs. at the baseline assuming similar level of standard deviation at the end of treatment with a two-sided 0.05 significance level using a paired t-test. We expect to have adequate power to detect this level of change for both the study arms since prior study has observed a decrease of at least $3 \log_{10} \text{vp/mL}$ with Oseltamivir alone in immune compromised patients [ref: Infect Dis Ther (2019) 8:613–626]. For the second co-primary endpoint, i.e., the between arm differences in change in viral loads, 15 patients per arm will allow 80% power to detect effects size as small as 1.1 standard deviation at a two-sided 0.05 significance level. It is likely the study is under-powered but is expected to generate meaningful preliminary efficacy data [Machin, D, Campbell, M.J., Tan, S.B, Tan, S.H. 2018. 'Sample Sizes for Clinical, Laboratory and Epidemiology Studies, Fourth Edition', Chapter 16. John Wiley and Sons. Hoboken, New Jersey.].

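### The between-arm co-primary contrast is not adjusted for baseline viral load or the stratification factors; ANCOVA on data already collected would give a tighter interval at almost no cost.

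*Combined protocol and SAP*

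**What the plan says.** Statistical Considerations restricts the primary analysis to "a modified intention-to-treat (ITT) principle for patients with viral loads measurements at both the baseline and day 10". It assesses the second co-primary by "estimating the differences in the magnitude of change in viral RNA loads from baseline at the end of treatment between the two treatment arms", with 95% confidence intervals. It names no model or covariate for this estimate.

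Randomisation is stratified. Section 3.1 says "patients will be stratified by hospitalization status (yes or no), influenza type A (yes or no", and Section 4.3 repeats it: "patients will be stratified by hospitalization (yes or no), influenza type A (yes or no". Neither factor appears in any analysis.

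Section 2.1 defines the between-arm co-primary "as measured by (qRT-PCR, nucleic acid) and by Influenza plaque assay (replicating virus". The analysis text for that co-primary mentions viral RNA only. However, secondary endpoints 2 (qRT-PCR) and 4 (plaque assay) in Section 2.1 both cover the "Difference in change of influenza viral loads from baseline (day 1) at day 4, 7 and 10 between the two treatment arms". Statistical Considerations gives the secondary viral-load endpoints a mixed-effects repeated-measures model in patients with at least one relevant load. That model also names no baseline or strata terms.

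The same section says the sample size rests mainly on feasibility, that the study is probably under-powered, and that every between-arm comparison is exploratory.

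**The concern.** The between-arm contrast is the only primary comparison that isolates what baloxavir adds to oseltamivir. The within-arm test cannot do so, because the plan already expects a fall of at least 3 log10 on oseltamivir alone. The useful product of a 30-patient pilot is an estimate with an interval, and an unadjusted change score makes that interval wider than it need be unless baseline and day-10 loads are very highly correlated.

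The covariates cost nothing to obtain: baseline load is part of the endpoint, and both strata are known at randomisation. Naming the estimator before unblinding also prevents a choice between adjusted and unadjusted results once they have been seen.

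**Working it through.** **Inputs.** All come from Statistical Considerations: 15 per arm, two-sided 0.05, 80% power, SD about 3 log10 at baseline and similar at day 10, a within-arm detectable change of 2.33 log10, and a between-arm detectable effect of 1.1 SD. The correlation r between baseline and day-10 load is not stated, so it is varied. Power uses the noncentral t distribution.

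**1. The plan's own figures reproduce.**
- Paired t, 14 df: 80% power needs noncentrality 3.013, so 3.013/√15 = 0.778 SD, and 0.778 × 3 = 2.33.
- Two-sample t, 28 df: noncentrality 2.902, so 2.902 × √(2/15) = 1.06 SD, which rounds to 1.1.
- Implied correlation: SD of change = 2.33/0.778 = 2.995, so r = 1 − 2.995²/18 = 0.50. This may only reflect reuse of SD 3 for the difference, so 0.5 is a reference value and not a documented one.

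**2. Change score.** SE = 3 × √(2(1−r)) × √(2/15). At r = 0.5 this is 1.095. The detectable difference is 2.902 × 1.095 = 3.18 and the half-width 2.048 × 1.095 = 2.24.

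**3. ANCOVA with baseline and both strata.** SE = 3 × √(1−r²) × √(2k/15), on 30 − 2 − 3 = 25 df. With strata balanced by design, k = 1 + 1/26 = 27/26, the expected cost of chance imbalance in baseline load. At r = 0.5 the SE is 0.967. The detectable difference is 2.915 × 0.967 = 2.82 and the half-width 2.060 × 0.967 = 1.99. Power at 3.18 rises from 80% to 88.5%; an unadjusted change score would need about 19 per arm for that.

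**4. Range over r** (SD 3 at both times, log10 units, strata balanced):

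| r | Detectable, change score | Detectable, ANCOVA | Half-width, change score | Half-width, ANCOVA |
|---|---|---|---|---|
| 0 | 4.50 | 3.25 | 3.17 | 2.30 |
| 0.25 | 3.89 | 3.15 | 2.75 | 2.23 |
| 0.5 | 3.18 | 2.82 | 2.24 | 1.99 |
| 0.75 | 2.25 | 2.15 | 1.59 | 1.52 |
| 0.9 | 1.42 | 1.42 | 1.00 | 1.00 |

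**5. Imperfect balance.** Stratified blocks of 2 or 4 were simulated with assumed prevalences for (hospitalised, type A) of (0.5, 0.7), (0.3, 0.8) and (0.2, 0.9). Mean k was 1.051–1.072. At r = 0.5 the detectable difference is then 2.84–2.86 and the half-width 2.00–2.02. Power at 3.18, simulated directly with blocks of 4, was 87.1–87.9%. The break-even r is 0.91 with balanced strata and about 0.86–0.89 in these designs.

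**6. Smaller effects.** At r = 0.5, power for a 1 log10 difference is 14% with the change score and 17% with ANCOVA. For 1.5 log10 it is 26% and 32%.

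**7. Missing day-10 loads.** The documents give no loss rate. As an illustration, take r = 0.5, no true effect, and loss that rises with day-10 load. Loss of 20% in control against 10% shifts the change score by 0.12–0.18 and ANCOVA by 0.18–0.29. Loss of 30% against 10% shifts them by 0.24–0.35 and 0.37–0.56. Equal 10% loss shifts either by under 0.02. If loss depends on baseline load instead, the change score shifts by similar amounts in the opposite direction and ANCOVA by 0.01 or less. All of these lie well inside the half-widths in step 4 at r = 0.5.

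**The case against.** The strongest reply is that this is a preference. The contrast is unbiased under randomisation when no day-10 load is missing, the study is sized on feasibility, and the comparison is exploratory. That stands, and it limits the point to an inexpensive improvement.

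The gain is also modest where it matters most. On the plan's figures, control load at day 10 averages at most about 6.5 − 3 = 3.5 log10. A further fall of 3.18 would leave about 0.3, so 3.18 is close to the largest possible effect. For plausible moderate effects the study stays uninformative under either analysis. This stands too.

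Normality with no detection floor is assumed, and the documents give no rule for day-10 loads below detection. The exact figures are therefore approximate. A floor that compressed the day-10 spread would not by itself reverse the direction: with a day-10 SD of 2 and r = 0.5, the ratio of ANCOVA to change-score variance is 4 × 0.75/(9 + 4 − 6) = 0.43, against 0.75 with equal SDs.

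A reader might infer three stronger criticisms, which the documents do not support:
- **No scale is given.** The first co-primary uses log-transformed loads and the power inputs are in log10, so the scale of the between-arm change is reasonably inferred.
- **Plaque assay is left without a between-arm analysis.** Secondary endpoint 4 and the mixed model already plan a day-10 plaque contrast. Only the co-primary analysis text omits it.
- **The complete-case rule biases the result.** It is set in advance and can bias the contrast only if load-related loss differs by arm. No loss rate is given, and the wider set in the secondary mixed model partly covers the gap.

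**Conclusion.** The point holds as a precision gain worth taking. The stated power figures are right and the contrast is valid; nothing in the plan is invalidated, and no confirmatory error rate is at stake.

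The size rests on SD 3 at both times, 15 evaluable patients per arm, roughly normal log10 loads, and an unstated correlation. At r = 0.5 the interval narrows by about a tenth (2.24 to 1.99–2.02) and the detectable difference falls from 3.18 to 2.82–2.86. The gain grows as r falls and is gone near 0.9. It comes from baseline load: no benefit from the strata terms themselves can be shown from the documents, and the calculation counts only their cost.

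ANCOVA does not repair loss that depends on the day-10 load. In that setting it shifts somewhat more than the change score, so a sensitivity analysis belongs beside it.

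**What to change.** Before unblinding, add to the analysis plan:

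- **Main between-arm estimate:** ANCOVA on log10 day-10 load, with baseline log10 load, hospitalisation and influenza type A as covariates, reported with its 95% confidence interval. Apply the same model to the plaque assay named in this co-primary.
- **Supporting only:** the day-10 contrast from the planned mixed model with the same covariates. This needs days 4 and 7 to be quantified. Section 3.1 lists swabs on days "4, 7 and 10 for viral quantitation and viral sequencing", and Section 2.1 has endpoints at days 4 and 7, whereas Section 4.2.1 says "Viral RNA in pre- and last post-treatment swab samples will be extracted using conventional RNA extraction kit". Reconcile these passages first.
- **Supporting only:** a sensitivity analysis for deaths and missing day-10 loads, for example a worst-rank analysis.
- Keep the exploratory label.

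The cost of the main change is wording and analysis code, since the baseline and day-10 swabs and both strata are already planned. The statistical price is up to three degrees of freedom, with little or no gain if r is about 0.9 or higher (from about 0.86 in the simulated blocked designs).

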Participants will assess the severity of 7 influenza-associated symptoms (cough, sore throat, headache, nasal congestion, feverishness/chills, muscle/joint pain, and fatigue) on a 4-point scale (0 = no symptoms, 1= mild, 2 = moderate, and 3 = severe) as specified in section 4.5.7. Improvement is defined as: improvement pre-existing symptoms (i.e cough, fatigue, or muscle/join pain that existed prior to influenza) that were worse at baseline and improve at least 1 point from baseline; pre-existing symptoms not worse at baseline that maintain baseline severity; and new symptoms that are alleviated, defined as a symptom score of non (0) or mild (1).

Once all patient's influenza symptoms are alleviated, maintained, or improved (hereafter all will be called 'improvement') as defined above, the endpoint will be reached.

6. **Percentage of patients who experience each influenza-related complication** (hospitalization, death, sinusitis, otitis media, bronchitis, and radiologically-confirmed pneumonia) as an adverse event after the initiation of study treatment symptoms [symptoms [Time Frame: From Day 1 pre-treatment up to Day 30].
7. **Time to Return to Preinfluenza Health Status** [Time Frame: From Day 1 pre-treatment up to Day 30]. Participants will be asked to record their preinfluenza health status on a scale from 0 (worst possible health) to 10 (normal health [for someone same age and condition]), and their health status at baseline and every day after initiation of study treatment on the same scale as specified in section 4.5.7. Return to preinfluenza health status is defined as time from the initiation of the study treatment to the first time when the health status score was equal to or higher than the preinfluenza health status score.
8. **Time to viral clearance**, as assessed by difference in Percentage of Participants Positive by Influenza plaque assay and qPCR at each time-point (in each treatment group) The definition of the time to sustained cessation of infectious virus detection is the time

between the start of treatment and when virus titer remained below the detection limit on all subsequent sampling time points.

9. Measure treatment-emergent variants of neuraminidase and polymerase known to confer antiviral resistance to oseltamivir in each arm by direct next-generation sequencing symptoms [Time Frame: From Day 1 pre-treatment up to Day 30]

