For secondary viral loads related endpoints, summary statistics in terms of mean, standard deviation, median and range will be calculated for each arm at each time points among patients with relevant measurements. Longitudinal analyses using mixed effects repeated measures will be used to model the mean viral loads overall time. Contrasts of interest including between arm differences will be explored using simultaneous tests of general linear hypotheses. If normality is a concern, log-transformed and standardized viral load data will be used. Longitudinal analysis will be carried out among patients with at least one relevant viral load measurement. Kaplan-Meier estimates will be generated for time to events endpoints such as time to Improvement of Individual Influenza Symptoms, the time to viral clearance and time to return to preinfluenza health status for each study arm. Between study arm difference in these endpoints will be explored using the generalized Wilcoxon test.

Categorical data such as the occurrence of treatment-emergent variants of neuraminidase and polymerase by direct next-generation sequencing and AE's will be summarized in terms of counts and proportions separately for each arm.

Between arm difference in the categorical variable will be explored using Fisher's exact test. The study is likely will not have adequate power to detect between arm differences and all the between arms comparisons are considered exploratory. Summary statistics generated for study endpoints for each arm will provide useful information for planning future studies.

The power calculations were performed using PASS 15 Power Analysis and Sample Size Software (2017). NCSS, LLC. Kaysville, Utah, USA, ncss.com/software/pass. All comparisons will be two-tailed, with a significance level at 0.05 and 95% confidence intervals will also be reported. All analyses will be performed in SAS Version 9.4 (2019), SAS Institute, Inc., Cary, NC; and R Version 4.0.4 (2021).

Note: The statistical considerations section was written by [name], MS, and revised by [name], in the Division of Biostatistics, Department of Population Health Sciences, Weill Cornell Medicine.

Influenza sequence analysis will be performed by [name], Director of Systems Genomics Section at the Laboratory of Parasitic Diseases of NIAID/NIH and expert in Influenza evolution.

No interim analysis is planned for this study

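### The primary comparison of log viral RNA change to day 10 has no rule for undetectable results, so its size and power depend on an unstated choice

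*Combined protocol and SAP*

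**What the plan says.** Section 2.1 names two co-primary endpoints: the day 1 to day 10 change in viral RNA load by qRT-PCR, and the between-arm difference in that change. The second endpoint also names the plaque assay.

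Statistical Considerations restricts the primary analysis to patients with viral load measured at both baseline and day 10. Within each arm, "Difference in log transformed viral RNA loads measured at the end of treatment and at baseline will be evaluated using paired t-test" or, alternatively, the Wilcoxon signed rank test. For the between-arm endpoint the plan estimates the difference in change with a 95% confidence interval and names no model or test. It adds: "All comparisons will be two-tailed, with a significance level at 0.05 and 95% confidence intervals will also be reported".

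A detection limit appears only in secondary endpoint 8 (section 2.1), where cessation of infectious virus means that "virus titer remained below the detection limit on all subsequent sampling time points". That definition concerns infectious titre, but the same endpoint also reports the percentage positive by plaque assay and by qPCR at each time point. Section 3.1 foresees that some patients will have cleared by day 10: "Patients who will not clear the virus by day 10 will perform additional NP swabs at these visits". No section gives a limit for either assay, says whether an undetectable day-10 result counts as a measurement, or says what value it takes on the log scale.

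**The concern.** An undetectable load has no logarithm. A plain comparison of log changes must therefore leave such a patient out or substitute a number. Leaving the patient out removes the best virological outcome. Substituting the limit understates the fall. If the combination works, more of its patients are affected than controls, so the difference between arms is distorted and not merely noisier.

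The choice may also be made late. Section 4.2.1 has the swabs assayed at the end of the clinical period, and section 4.3 breaks the blind when the last patient finishes follow-up. Without a written rule, the handling that determines a co-primary estimate could be settled with allocation known.

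**Working it through.** **Inputs from the plan.** Allocation is "Participants will be randomly assigned (1:1) to either baloxavir + oseltamivir or baloxavir-matched placebo +oseltamivir", with 15 per arm and two-sided 0.05. Mean baseline is 6.5 log10 with SD about 3, "assuming similar level of standard deviation at the end of treatment". The fall on oseltamivir alone is at least 3 log10. The between-arm detectable effect is 1.1 SD.

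**Assumed.** Assay limit 1, 2 or 3 log10; bivariate normal loads; correlation 0.5; baseline above the limit, because entry requires a positive PCR.

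**Step 1: reproduce the plan's power.**
- SD of change = 3 × √(2(1 − ρ)). With ρ = 0.5 this is 3; with ρ = 0 it is 4.24.
- Within arm, paired t, n = 15, d = 2.33/3: power 79.9%, detectable change 2.334 log10. The plan's 2.33 is reproduced with an SD of change of 3, so ρ = 0.5 agrees with it. At ρ = 0 power would be 51%.
- Between arms, two-sample t, 15 per arm, d = 1.1: power 82.8%; the 80% point is 1.06 SD. The plan's 1.1 is this rounded up. In log10 units, 1.1 × 3 = 3.3.

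The stated figures reproduce and contain no allowance for an assay limit.

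**Step 2: share of patients below the limit at day 10.** The control mean is 6.5 − 3 = 3.5. At a true difference of 3.3 the combination mean is 0.2. The share below limit L is about Φ((L − mean)/3). For L = 2 this is Φ(−0.5) = 31% and Φ(0.6) = 73%. Keeping baseline above the limit lowers these slightly, to 28% and 71%.

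**Step 3: simulate the two usual handlings** (unadjusted t-test on change, true difference 3.3 log10; differences shown as size of extra fall):

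| | L = 1 | L = 2 | L = 3 |
|---|---|---|---|
| Below limit, control / combination | 19% / 59% | 28% / 71% | 39% / 80% |
| Set to limit: estimate | 2.05 | 1.67 | 1.30 |
| Set to limit: power | 52–54% | 40–44% | 31% |
| Dropped: estimate | 2.33 | 2.15 | 1.99 |
| Dropped: power | 28–35% | 24–25% | 16–17% |

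Ranges span repeated runs. Uncensored power was 84–85%, a little above 82.8% because keeping baseline above the limit narrows its spread. Attenuation when set to the limit runs from 1 − 2.05/3.3 = 38% to 1 − 1.30/3.3 = 61%; when dropped, from 29% to 40%.

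**Step 4: does the direction always hold?** With no true effect (L = 2) the bias is 0.00 and the rejection rate about 5%. With SD 1.5 and a true 1.65, setting to the limit gives 1.41, 1.10 and 0.70, and dropping gives 1.37, 1.22 and 1.08. Coding undetectable as 0 log10 gives 2.45 to 2.55 at SD 3 (true 3.3), but 1.87 and 1.94 at SD 1.5 with L = 2 and 3 (true 1.65), which is inflation.

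**Step 5: alternatives at a true 3.3, L = 1 to 3.**

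| Method | Power, L = 1 | Power, L = 3 | Estimate |
|---|---|---|---|
| Set to limit, ANCOVA on baseline | 84–87% | 70–73% | 2.0 to 1.3 |
| Rank test on day-10 values, undetectable tied lowest | 78–82% | 71–75% | none |
| Left-censored model adjusted for baseline | 89–92% | 80–86% | about 3.2 to 3.4 |

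Rejection under no effect for the censored model was 4–9% across runs of 300 to 500 trials. Its likelihood-ratio test is approximate at this sample size.

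**The case against.** The strongest reply is that this is a pilot. The plan says it is probably under-powered and calls all between-arm comparisons exploratory. Clearance is analysed separately, by percentage positive and by time to viral clearance, so the benefit in patients who clear is not lost to the trial. This stands as a limit on the stakes. It does not remove the point: the between-arm difference is still co-primary, and the per-arm summaries are meant to inform later trials. A difference attenuated by 29% to 61% would mislead that planning.

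A second reply is that the Wilcoxon option or the mixed model covers the problem. The Wilcoxon option is within-arm only and still needs a value for undetectable results. The mixed model is for the secondary endpoints and has no censoring rule either.

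A third concerns the remedy. The simulated data obey the normal model that the censored regression assumes, so its good recovery is partly built in. At 3.3 log10 roughly 43–46% of combination values fall below 0 log10, and only about 3 to 6 of 15 are observed above the limit. The 5–95% range of the estimate at the highest limit is about 6.2 to 1.5. This stands, and is why a rank test belongs beside it.

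Four stronger readings are tempting and not supported:
- That the plan drops undetectable patients or sets them to a floor. It is silent.
- That it expects many to clear by day 10. Section 3.1 gives no rate, and sections 1.3 and 3.3.3 stress prolonged shedding.
- That bias is always towards zero. Step 4 shows otherwise.
- That censoring alone costs the power. Baseline adjustment restores much of it even with values set to the limit.

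**Conclusion.** The omission is real and material at the plan's own planning values. Under a true 3.3 log10 difference and an assumed limit of 1 to 3 log10, setting undetectable results to the limit gives about 2.0 to 1.3 log10 with about 54% to 31% power. Dropping them gives about 28–35% power, falling to about 16%, against about 85% uncensored. With no true effect there is no bias, so the harm is a distorted estimate and lost power, not false positives.

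Most of the recoverable power comes from adjusting for baseline; the censored model mainly removes the attenuation. The size depends on the assay limit, the SD of change and the true effect. The first two are not stated, and 3.3 log10 is a detectable difference, not an expected one. Confidence is moderate. The plan should be changed, but the stated power calculation is not itself wrong.

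**What to change.** Before the samples are assayed and the blind is broken, add to Statistical Considerations:

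1. The lower limits for qRT-PCR and for the plaque assay.
2. A statement that an undetectable day-10 result counts as a measurement and is never dropped.
3. For the between-arm analysis, day-10 log10 load by arm, adjusted for baseline log10 load, with undetectable values left-censored at the limit. This replaces the unadjusted comparison of change scores.
4. Alongside it, a rank test of day-10 values with undetectable results tied lowest.
5. Substitution at the limit as a sensitivity analysis.
6. The same left-censoring in the repeated-measures model for the secondary viral load endpoints.

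The cost is plan wording and modest programming, with no extra patients or samples. The downside is that at 15 per arm the censored estimate is imprecise and leans on normality; the rank test covers the inference if that assumption fails.
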